
PK analysis:
 
Ir-CPI individual and mean plasma concentrations at each sampling time point will be presented by listings and descriptive summary statistics including means, geometric means, medians, ranges, standard deviations and coefficients of variation. Individual and mean plasma concentrations versus time will be plotted on linear and log-linear scales. Descriptive statistics and graphs will be also performed for the plasma PK parameters.
 
Relevant plasma PK parameters will be derived for the parent by compartmental methods for plasma and tabulated along with descriptive statistics.
 
The linear dose-proportionality of C_{max}, AUC_{0-6} and AUC_{inf} (if applicable) will be assessed using an exponential regression model ("power model") in part 1 and part 2.
 
PD analysis:
 
Descriptive statistics will be provided on values and changes from baseline for each time-point.
 
Exploratory PK-PD analysis:
 
As an exploratory analysis, evaluation of the relationship between doses and concentrations of Ir-CPI and the change from baseline in coagulation parameters will be investigated.
 
Exploratory Biomarkers Analysis
 
Descriptive statistics will be provided on values and changes from baseline for each time-point.
 
Presence of ADA will be described by time-point until D180.
 
Safety Analysis
 
All AEs and treatment-emergent AEs will be described overall and by preferred term and system organ class until D180. Summary descriptive statistics will be provided for the other safety parameters.
 
Supplemental ADA samplings ("long-term follow-up of ADAs"):
 
ADA results from the additional samplings after D180 will only be listed and appended to the final Clinical Study Report (CSR). SADRs and related information after D180 will only be collected in the PV database.

4. See laboratory safety parameter assessments (section 9.7.6) for list of tests to be run.
5. See laboratory safety parameter assessments (section 9.7.6) for list of tests to be run.
6. Physical Examination (including basic neurological testing for isocoria, light reflexes, gait and balance) should be performed at screening, on D-1, then 24h postdose (D2) and at the discharge visit.
7. An abbreviated physical exam should be performed at 8h postdose on D1.
8. Supine vital signs should be measured after 5 minutes of rest in a supine position and include body temperature, resting pulse rate, and blood pressure: at screening, then from D1 to D4, vital signs should be done predose, 60min, 2h, 4h, 6h, 8h, 10h, 12h, 24h, 48h, 72h postdose, and then at the discharge visit (D10+/-2d).
9. Cardiac monitoring using telemetry (3-lead minimum and including SpO₂) is to be performed from 1h predose up to 12h postdose.
10. ECG should be done at screening, then on D1 (predose, 2h, 4h, 6h, 8h, 12h), 24h (D2), 48h (D3), 72h (D4) postdose and at the discharge visit. Timing can be adjusted based on emerging PK data.
11. See laboratory safety parameter assessments for list of tests to be run (section 9.7.6): screening, then from D1 to D4: Predose (D1), 24h (D2), 72h postdose (D4), and then at the discharge visit.
12. Participants will be asked at baseline if they have been previously exposed to tick bites. At the discharge and extra-ambulatory visits performed for ADA analysis, the participants will be asked if they have been exposed to tick bite since the previous visit (response recorded as yes/no/unknown). If the answer is yes, then the participant will be asked to provide information on treatment (e.g. antibiotics) and on presence of erythema migrans and other signs or symptoms.
13. The baseline chemistry (predose sample) will also contain an extra archive serum sample for anti-Borrelia serology testing (IgG and IgM) as backup to test for anti-Borrelia antibodies due to previous exposure via potential tick bites.
14. Safety aPTT (local lab) at screening, then on D1, predose, then 2h, 4h, 6h, 8h, 12h, D2 (24h), D3 (48h) and D4 (72h) postdose and at the discharge visit.
15. Urinalysis at screening, then predose (D1), 24h (D2), 72h postdose (D4) and at the discharge visit. See laboratory safety parameter assessments for list of tests to be run (section 9.7.6).
16. All participants will receive a single intravenous dose of Ir-CPI/Placebo given as a 6-hour infusion. Post dose is measured after the beginning of infusion. A light breakfast (2 slices of bread with ham or cheese and jam, glass of water) can be given between 2h and 1h before start of infusion. Lunch will be served after completion of the infusion.
17. Cluster A (central lab): the effect of Ir-CPI on PD aPTT (central lab) (not to be confused with safety aPTT) and on FXI/FXII activities will be measured on D1: pre-dose, then at 30min, 60min, 90min, 2h, 4h, 6h, 6h30, 7h, 7h30, 8h, 10h, 12h, 16h post-dose, then on D2 (24h), D3 (48h), D4 (72h), D5 (96h) and discharge visit. In case of infusion less than 6 hours and besides assessment at predose, 30 min, 60 min, 90 min, 2h and 4h after start of infusion, Cluster A (central lab) parameters should be measured at the end of infusion, then 30 min, 60 min, 90 min, 2h, 4h, 6h, 10h, then 18h, 42h, 66h and 90h after the end of infusion and then at the discharge visit.
18. Cluster B (local lab) the effect of Ir-CPI on PT (sec and INR), D-dimers, fibrinogen, hsCRP and TNF α will be measured on D1, predose then at 2h, 4h, 6h, 8h, 12h post-dose, on D2 (24h post-dose), D3 (48h) and D4 (72h) and discharge visit. In case of infusion less than 6 hours and besides assessment on D1 at predose and at 2h and 4h after start of infusion, Cluster B (local lab) parameters will be measured at the end of infusion, then 2h, 6h, 18h, 42h and 66h after the end of infusion and then at the discharge visit.
19. CysC (central lab) will be collected at screening, then from D1 to D4: Predose (D1), 24h (D2), 72h postdose (D4), and then at the discharge visit.
20. Blood samples for Ir-CPI PK will be done on D1, pre-dose and at 30min, 60min, 90min, 2h, 4h, 6h, 6h30, 7h, 7h30, 8h, 10h, 12h, 16h, then D2 (24h), D3 (48h), D4 (72h) and D5 (96h) post-dose (after start of infusion). In case of infusion less than 6 hours, blood sample for Ir-CPI pharmacokinetics will be done at the end of infusion then 30min, 60min, 90min, 2h, 4h, 6h, 10h, 18h, 42h, 66h and 90h after end of infusion.
21. ADA analysis sample: pre-dose on the day of infusion, at the discharge visit, on D30 and on D90.

22. D180 only if ADAs are detected in the D90 samples.
23. Urine collections for PK assay are to be done at these intervals predose, [0-6h[, [6-12h[and [12-24h] after start of infusion. Urinary NGAL, microalbuminuria and KIM-1 will be assessed.
24. Samplings will be performed until the participants reach a negative status, until they show the same ADA titre result for 3 samplings in a row, or up to a maximum of 5 years after D180, whichever comes first. Otherwise, samplings will be performed every 3 months for the first year then every 6 months up to a maximum of 5 years after the D180 ambulatory visit. As the D180 visit was performed on the same day for all participants (and not according to D1 of a given cohort), these additional samplings will be performed in the same time-frame for all concerned participants. If a planned sampling is missed, the subsequent samplings can still be performed.

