
Number of participants:
 
Part 1: Approximately forty (40) healthy male participants will be enrolled in 5 sequential panels. Each panel will have 8 participants (6 active: 2 placebo). The fifth group will be optional depending on the PK and PD data obtained in the previous groups.
 
Part 2: Approximately twenty-four (24) healthy male participants will be enrolled in 3 sequential panels. Each panel will have 8 participants (6 active: 2 placebo).
 
In the end, the optional fifth group in part 1, and part 2 were not performed.

Rationale for Number of Participants:
 
The number of participants is not based on statistical power considerations. A sample size of 8 participants per cohort (i.e., 6 active and 2 placebo) was chosen based on the design of similar studies and is considered adequate to provide an initial assessment of the safety and tolerability profile of Ir-CPI.

Number of study centres:
 
1

Duration of treatment:
 
The study duration for each participant for the main study part (from the screening visit until the discharge visit) will be approximately 6 weeks. Participants will be followed up until D90 (or D180) for immunogenicity testing. The total study duration will be approximately 18 weeks in total for a given

Name of Company: BIOXODES SA [name] ; [name]; [name]; BELGIUM
				

Name of Finished Product: NA
				

Name of active ingredient: Ixodes ricinus-Contact Phase Inhibitor (Ir-CPI)
				

participant, and up to 31 weeks in case of D180 visits. Supplemental ADA samplings (“long-term follow-up of ADAs”): Additional samplings for immunogenicity testing may be performed until the participants reach a negative status, until they show the same ADA titre for 3 samplings in a row, or up to 5 years after the end of the study in participants with positive ADA results at D180 whichever comes first.
				

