Demographic and Safety Assessments Screening and demography assessment will cover demography (including race and ethnicity), inclusion / exclusion criteria, medical and medication history, drug / alcohol screen and serology. Safety will be evaluated from: reported AEs, physical examinations (the complete examination includes basic neurological testing for isocoria, light reflexes, gait and balance), vital signs, telemetry including SpO ₂ , weight, presence of occult blood in faeces (Hemocult® test), supine 12-lead ECG, serum chemistry, haematology, coagulation aPTT (safety aPTT), laboratory safety urinalysis, and monitoring for concomitant medications. Exposure to potential tick bites will be monitored (extra serology sample for archiving at baseline for anti-Borrelia IgG and IgM assays, and question asked to participants on D1, at the discharge visit, and at the extra-ambulatory visits performed for ADA analysis). AEs related to bleeding (e.g. positive Hemocult® testing, gingival bleeding, bruising/haematoma, conjunctival bleeding, prolonged bleeding after trauma) will be considered as adverse events of special interest (AESI). Also considered as AESI are all infusion site reactions, including hypersensitivity reactions that would occur during or after study drug administration. AEs will be monitored from the screening visit until the last extra-ambulatory visit.
Statistical methods: Statistical analysis of clinical parameters will be performed under the responsibility of Biotrial.

Name of Company: BIOXODES SA [name] ; [name]; [name]; BELGIUM
Name of Finished Product: NA
Name of active ingredient: Ixodes ricinus-Contact Phase Inhibitor (Ir-CPI)

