5.4. End of Study Definition and Duration of Participation

The end of the study is defined as the date of the last visit of the last participant in the study.

Therefore, the end of the study is defined as either the date on which the last study participant completes the Month 3 visit (D90) for immunogenicity testing or, if for a given participant ADAs are detected, the date on which the last study participant completes the supplementary Month 6 visit (D180), whichever is later.

The study duration for each participant for the main study part (from the screening visit until the discharge visit) will be approximately 6 weeks. Participants will be followed up until D90 (or D180) for immunogenicity testing. The total study duration will be approximately 18 weeks in total for a given participant, and up to 31 weeks in case of D180 visits.

Following the completion of the study, a 3-month exclusion period will apply to the participant before they are allowed to take part in another clinical study.

Supplemental ADA samplings (“long-term follow-up of ADAs”):

Extra ambulatory samplings that will be performed after D180 in participants positive for ADAs at D180 will be considered as occurring after the end of the study: these samplings are required for long term follow-up of the potential impact of ADAs, but based on the clinical data accumulated in this study, no SAE or AE or AESI has been reported as associated with the occurrence of ADAs. The results of these additional samplings will be not collected in the eCRF but in source documents only, and will be added to the final Clinical Study Report (CSR) as an appended additional listing.

Participants followed up after D180 for ADA analysis will be authorised to participate in other clinical trial studies except for clinical trials with biologicals (e.g. antithrombotic molecule acting on FXI and FXII).

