9.6.1. Documentation and Treatment of Adverse Events by the Investigator

All AEs, including AESIs and SAEs, occurring within the period of observation for the clinical study must be recorded.

The **period of observation** for the collection of AEs extends from the time when the participant gives informed consent until the last study visit. For all participants, this period will be extended to follow-up on all on-going AEs after the end of the treatment period, until all AEs are finally resolved or it is medically justifiable to stop further follow-up (e.g., a chronic condition has been reached, i.e. stabilization of symptoms).

There is no time limit on the collection of SAEs that are considered related to IMP. If the investigator detects an SAE in a study participant after the end of the period of observation, and considers the event possibly related to prior study treatment or procedures, he or she must contact the Pharmacovigilance (PV) contact of the Sponsor to determine how the SAE should be documented and reported.

The description of the AEs (including date and time of onset and resolution when applicable) must be documented as soon and as completely as possible on the “Adverse Events” pages in the eCRF. Follow-up information must be entered as soon as available.

The following will also be specified:

- Seriousness including criteria for seriousness;
- Severity
- Action taken;
- Relationship to treatment;
- Additional therapy;
- If it was the cause of study discontinuation;
- Outcome.

AEs that occur during the study should be treated by established standards of care that will protect the life and health of the participants. If such treatment constitutes a deviation from the protocol, the participants should be withdrawn from the study and the reason must be documented in the eCRF.

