- In urine: Urinary microalbumin, Kidney Injury Molecule (KIM-1), Urinary Neutrophil Gelatinase-Associated Lopocalin (NGAL).

Samples for D-dimers, fibrinogen, PT, hsCRP and TNF α will be collected at pre-dose on D1 and then 2h, 4h, 6h, 8h, 12h post-dose, at 24h (D2), at 48h (D3), at 72h (D4) discharge visit (D10 \pm 2 days) (see section 16.1).

CysC samples will be collected at screening, then from D1 to D4: pre-dose (D1), 24h (D2), 72h postdose (D4), and then at the discharge visit (D10 \pm 2 days) (see section 16.1).

ADA analysis samples will be collected at pre-dose on the day of infusion, at the discharge visit (D10 \pm 2 days), on D30 and on D90. If ADAs are detected in D90 samples, ADA analysis samples will be collected also at D180 (see section 16.1).

Urine collections will be done at these intervals pre-dose, [0-6h], [6-12h] and [12-24h] after start of infusion. Urinary NGAL, microalbuminuria and KIM-1 will be assessed (see section 16.1).

For each parameter, descriptive statistics will be provided by treatment group on absolute values and changes from baseline for each measurement time. Graph over time by treatment group will be also produced.

Presence of ADA (and their titration for ADA+ samples) and sub-classes determination (isotype) will be described by treatment group and measurement time.

All exploratory parameters will be listed.

13. Safety data

The safety analyses will be performed on the SS.

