13.1. Adverse events

Adverse events, including pre-treatment events, will be recorded from the time of consent through the end of the study.

Adverse events will be coded according to MedDRA Version 22.0.

A treatment-emergent adverse event (TEAE) is an adverse event that occurs after IMP dosing or that was present prior to dosing but was exacerbated between dosing during a treatment period and the end of the study.

Adverse events (including AESIs) will be summarised in tables as follows [overall and by System Organ Class (SOC) and Preferred Term (PT)]:

- Number and percentage of subjects with at least one adverse event and number of occurrences of an adverse event by treatment group and overall,
- Number and percentage of subjects with at least one TEAE and number of occurrences of a TEAE by treatment group and overall,
- By intensity, with the number and percentage of subjects with at least one TEAE and number of occurrences of a TEAE by treatment group and overall,
- By causality, with the number and percentage of subjects with at least one TEAE and number of occurrences of a TEAE by treatment group and overall.

If there are only a few adverse events (≤ 10), only a listing will be generated.

All adverse events reported in the Case Report Form (CRF) will be listed with the SOC, the PT and the Investigator's verbatim. All TEAEs will also be listed with the SOC and the PT. An additional listing will be provided for AEs leading to death and other serious and significant AEs (SAEs or AEs leading to study withdrawal).

Note: In case of a change of intensity or causality for an event during the treatment period, the intensity will be the highest recorded intensity and the causality will be the highest likelihood recorded.

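### TEAE tables use crude counts over follow-up of about 90 or 180 days, depending on the D90 antibody result; a table cut at D90 would give all groups the same window (minor)

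*Protocol*

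**What the plan says.** **Collection.** The protocol synopsis (Demographic and Safety Assessments) states: "AEs will be monitored from the screening visit until the last extra-ambulatory visit". Protocol section 9.6.1 says the observation period "extends from the time when the participant gives informed consent until the last study visit".

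**Tabulation.** SAP section 13.1 plans this summary: "Number and percentage of subjects with at least one TEAE and number of occurrences of a TEAE by treatment group and overall". SAP section 6.2 pools placebo across cohorts. Neither section 13.1 nor the table list in section 16.4 sets a cut-off day or a person-time denominator. The only stated limit is in the protocol synopsis: "All AEs and treatment-emergent AEs will be described overall and by preferred term and system organ class until D180".

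**Who has a D180 visit.** The schedule-of-activities footnotes for cohorts A to C (22) and D to E (23) both read: "D180 only if ADAs are detected in the D90 samples". SAP section 12 agrees: "If ADAs are detected in D90 samples, ADA analysis samples will be collected also at D180". Protocol section 5.4 gives the resulting durations: "approximately 18 weeks in total for a given participant, and up to 31 weeks in case of D180 visits".

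**When D180 took place.** Footnotes 24 (cohorts A to C) and 25 (cohorts D and E) report that it was held on one calendar day, not counted from each cohort's day of dosing. Protocol section 3.3 requires at least 7 days between the first participants of consecutive panels.

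**Related rules.** SAP section 6.2 bases percentages on observed values, and its next sentence puts missing values in the denominator. The pharmacodynamic set (SAP section 7.1, protocol section 10.2.3.1) requires study completion, although the last PD samples are taken at the discharge visit.

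**The concern.** A crude percentage of participants with an event rises with time at risk. Here time at risk is partly decided after dosing, by the D90 antibody result, and antibody formation may be commoner on active drug than on placebo. Active groups could then show more participants with a TEAE simply because more of them were asked about events for another three months. A single calendar day for D180 would also follow earlier, lower-dose cohorts longer than later ones. Pooling placebo removes the partial protection of comparing each cohort with its own two placebo participants.

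Adverse events are part of the primary endpoint, and this table is where dose groups and placebo will be compared. The SAP already applies the principle elsewhere: section 9.2.1 adds an AUC to 96 hours so that all four cohorts can be compared, because cohort D is sampled for longer. Adverse events have no equivalent.

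**Working it through.** **1. The plan's own durations.** Screening is up to 28 days; the visit windows are D90 ± 7 and D180 ± 7.

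- Without D180: (28 + 90 + 7)/7 = 17.9 weeks (stated: about 18).
- With D180: (28 + 180 + 7)/7 = 30.7 weeks (stated: up to 31).

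The two durations are therefore D90 follow-up and D180 follow-up. After dosing they are nominally 90 and 180 days, a ratio of 2.0 (from 173/97 = 1.78 to 187/83 = 2.25 within the windows).

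**2. Effect of the D90 condition.** The documents give no human post-dose ADA or adverse event rates, so everything in this step is assumed, with no drug effect. Let r be events per participant per 90 days, f the fraction positive at D90, and L the relative event load of days 90 to 180:

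P(at least one TEAE) = (1 − f)(1 − e^(−r)) + f(1 − e^(−r(1 + L)))

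L = 1 is a constant rate. L = 0.2 × 90/80 = 0.225 applies if 80% of 90-day events fall in the first 10 days and the later rate continues.

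| r | f = 0 | f = 0.5, L = 1 | f = 0.5, L = 0.225 |
|---|---|---|---|
| 0.2 | 18.1% | 25.5% (+7.4) | 19.9% (+1.8) |
| 0.5 | 39.3% | 51.3% (+11.9) | 42.6% (+3.2) |
| 1.0 | 63.2% | 74.8% (+11.6) | 66.9% (+3.7) |

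The range is about 2 to 12 points, or 0.1 to 0.7 of 6 participants. Event counts are 1 + 0.5L times as high: 1.11 to 1.50. With 1 of 6 positive the range is 0.6 to 4.0 points; with 6 of 6 it is 3.6 to 23.9.

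SAP section 13.1 gives only a listing when there are 10 or fewer events. At r = 0.2, 32 participants yield 32 × 0.2 = 6.4 events over 90 days, or 8.8 with half of the 24 active participants followed to D180 at a constant rate. On average no table would exist there. Where a table is likely (r of 0.5 or more), the range is 3.2 to 11.9 points.

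**3. Effect of a single calendar day.** From the first participant of A to the first of D there are three gaps of at least 7 days: 3 × 7 = 21 days. That exceeds the 14-day span of D180 ± 7, so not every attender could be in window. Take D at 180 days and A at 201. If only D90-positives attended, half in each cohort, L for cohort A becomes 111/90 = 1.233 (constant rate) or 0.2 × 111/80 = 0.2775 (early clustering). At r = 0.5, A reads 53.3% against 51.3% for D, or 43.3% against 42.6%: a further 2.0 or 0.7 points between cohorts.

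**4. When the windows are equal.** If nobody is positive at D90, all planned follow-up ends at D90. If everybody is positive and D180 is timed from dosing, all ends at D180. Neither is guaranteed.

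**5. SAP section 6.2.** Six treated, one missed sample, two ADA-positive: 2/5 = 40% on observed values, 2/6 = 33% with the missing value in the denominator. Both sentences cannot be followed.

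**6. Pharmacodynamic set.** A participant with every PD sample through discharge who later withdraws can be excluded as not having completed. One exclusion is 1/6 = 17% of a dose group. ADA and biomarker tables use the same set.

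**The case against.** The strongest answer is that little is at stake. The analysis is descriptive and the sample size is not based on power. Protocol sections 3.1 and 3.3 expect the most severe and acute reactions during or very soon after infusion, and section 5.4 reports no adverse event associated with ADAs. Attendance by visit, study day in the listings and TEAEs by causality let a careful reader reconstruct a common window. All of this stands and sets the severity, although none of these outputs changes the percentages in the table.

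The magnitudes are also assumed. The protocol's background data on immunogenicity do not address positivity at D90, and zero positivity on placebo ignores the 2 of 50 healthy Belgian donors who tested positive (section 3.2). Using 4% for placebo at r = 0.5 lowers the constant-rate difference only from 11.9 to 11.0 points.

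A reader might infer that no reading of the plan can give a common window. That is too strong: step 4 shows two exceptions, and D90 is planned for everyone. A reader might also infer that all participants attended D180 on one day. That conflicts with the footnotes restricting D180 to D90-positives; the more natural combined reading is that only those participants came, on one day. Nor does SAP section 13.1 itself set a D180 cut-off; it records events to the end of the study.

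On the pharmacodynamic set, the SAP leaves final membership to the blind review meeting, which can repair individual cases. The written rule should not depend on that.

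**Conclusion.** The point holds as a minor one. The plan guarantees no common window for the TEAE comparison: follow-up is about 90 or 180 days according to a post-dose antibody result, and among D180 attenders it differs by at least 21 days between cohorts A and D if all attended on one day. The effect is confined to late events. Its size cannot be obtained from the documents; about 2 to 12 percentage points rests on assumed event rates, no drug effect, and half of 6 active participants positive against no placebo participants.

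The documents do not support a reading that the main safety conclusion is threatened. Events near the infusion fall within everyone's follow-up and no test is planned on adverse events. The denominator contradiction in SAP section 6.2 and the completion requirement in the pharmacodynamic set are separate wording defects that stand on the text alone; they do not raise the severity of the follow-up point.

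**What to change.** 1. Add a TEAE table from dosing through the D90 visit as the between-group summary. Show later events in a separate table or listing, with the number followed and days since dose, so that they stay visible. Protocol section 10.1.3 puts the data lock-point at D180 and treats data as unblinded from then, so label the table post hoc if it is added after unblinding.
2. Correct SAP section 6.2 to a single percentage denominator.
3. Remove the study-completion requirement from the pharmacodynamic set in SAP section 7.1 and protocol section 10.2.3.1. Keep the conditions on PD-relevant deviations and on having at least one post-baseline PD value.
4. Clerical: protocol section 5.1.1 times D180 from analysis, whereas the synopsis and section 5.1.2 time it from dosing; reconcile them. In SAP section 8.4, replace V11 with a study day, since V11 is D180 in cohorts A to C but D90 in cohort D (SAP section 3.4).

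The cost is one added table, one late-event table or listing, light reprogramming, and wording changes in the SAP and in one protocol section. No new data are needed. The small drawback is that late events leave the main comparison table, which is why they need their own output.
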